8. RESEARCH QUESTION AND OBJECTIVES

The overall goal of this study is to understand the patient characteristics, treatment patterns, and clinical outcomes of ALK+ NSCLC patients treated with alectinib in US community oncology practices. To efficiently and effectively address research questions, we will leverage both the structured and unstructured data of the EHR and execute the study in 2 phases. Phase 1 will consider a population of ALK+ NSCLC patients who received alectinib during the study intake period. For Phase 2, a sample of patients who received alectinib as front-line therapy will be selected for chart review.

The study plan utilizes structured data and unstructured (chart review data). For the landscape objectives in Phase 1, study data will originate from structured fields of the EHR, which are controlled and mapped data elements, and will be available ahead of chart review data. For the second phase, specific study objectives will be assessed among a subset of patients selected for chart review using both structured and unstructured data. In this phase, data will also be derived from unstructured fields in the EHR, such as providers' free-text notes, which can only be captured through a chart review.

Phase 1: Landscape Objectives (structured data):

These analyses will be performed for all study-eligible patients who received alectinib (in any line of therapy) during the study identification period. Results will be presented overall as well as for the subgroups of patients who received a subsequent therapy following alectinib:

- 1. Describe the demographic and clinical characteristics of ALK+ NSCLC patients who received alectinib overall, and stratified by subsequent treatment following alectinib
- 2. Characterize post-alectinib treatment patterns and sequencing of other ALK inhibitors; categorizing type of treatments received after alectinib
- 3. Estimate duration of therapy with alectinib and duration of therapy for post-alectinib treatment
- 4. Examine overall survival of patients post-alectinib stratified by subsequent treatment following alectinib

Phase 2: Chart Review Objectives (unstructured data):

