Death date	iKM structured data + limited access death master file (LADMF) + chart review	Clinical outcomes	Study observation period	Date of death will be captured from the LADMF as well as iKM. If dates conflict between the 2 sources, the LADMF date will be prioritized. If severe data discordance is observed (i.e., death is reported to occur prior to the index date), then the iKM death date will be used.
Vital status	iKM structured data + LADMF + chart review (derived)	Clinical outcomes	Study observation period	Patients without a date of death in either the LADMF or iKM will be assumed to be alive at the end of the study. Those with a date of death in either LADMF or iKM will be flagged as deceased.
ALK inhibitor (alectinib and stratified by subsequent treatment) duration of therapy (DOT)	iKM structured data + chart review (derived)	Treatment characteristics	Study observation period	An intent to treat approach will be used. DOT will be defined as duration of time (in months) between alectinib initiation and discontinuation, or the last administration date of alectinib, or start date of a subsequent ALK inhibitor, or evidence of new non-ALK inhibitor treatment (as a proxy for evidence of discontinuation) will be used as a stop date. There may be some patients who do not have evidence of discontinuation or who do not move on to a subsequent therapy.
				Descriptive statistics (mean, median) and K-M methodology will be calculated from initiation of alectinib, until evidence of discontinuation for any reason, including but not limited to a treatment stop date, a last alectinib administration date, evidence of new ALK inhibitor treatment or non-ALK inhibitor treatment, death or check-in in a hospice. Patients who do not have evidence of discontinuing, starting new therapy, or whose last prescription date is <30 days from the end of

Table 1. Study variables and operational definitions

Variable	Source(s)	Role(s) in	Period of	Operational definition
		study	measurement	
				the study period, will be censored at last visit date or end of study period.

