9.8.3. Statistical methods

Description of study enrollment

To be included in the study patients must meet each of the inclusion criteria and none of the exclusion criteria listed in Section 9.3.1. Counts of patients excluded for each criterion will be summarized.

Additionally, the counts of patients to be classified into the following subgroups will be presented⁵:

- Cohort A: All alectinib treated patients (overall population)
- Cohort B (Alectinib only cohort): Alectinib treatment ongoing, or discontinued and no subsequent treatment⁶
- Cohort C: Alectinib followed by treatment X (top 3 most frequent)
- Cohort D: Alectinib followed by treatment Y (top 3 most frequent)
- Cohort E: Alectinib followed by treatment Z (top 3 most frequent)

Description of patient demographic, clinical and treatment characteristics

Descriptive analyses will be conducted to evaluate the demographic, clinical and treatment characteristics overall, as well as for each of the study cohorts. Results will be reported in

⁵ Final cohorts will be decided upon sample size. Patients receiving chemotherapy after initiating alectinib will be included in the patient sample

⁶ Patients with ongoing alectibin treatment, patients who discontinued alectinib and patients who did not have a subsequent treatment may be analyzed as separate cohorts depending on sample size of patients

aggregate. Categorical variables (e.g., ECOG performance status) will be reported as frequency and percentage. Continuous variables such as age will be reported as mean, standard deviation, median and range (minimum-maximum). In the case of missing observations, the number and percentage of missing values will be reported.

For comparative analysis, i.e. comparing 2 or more treatment groups (e.g., ALK inhibitor sequences) or strata (front-line alectinib and non front-line alectinib), statistical significance will be reported with level of statistical significance based on p = 0.05 level as well as 95% confidence intervals.

Chi-square testing will be used to assess associations between categorical variables when patient counts for single cells within the results tables are greater or equal to 5. When distribution cannot be assumed to be Chi-square, then Fisher's exact test will be used. Depending on normality, Analysis of variance (ANOVA)/t-tests or Kruskall-Wallis tests will be used for continuous variables. An alpha level of 0.05 will be the primary criterion for statistical significance of this study.

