All descriptive tables will be presented for each of the study cohorts defined above and, as supported by the final sample size, stratified by front-line alectinib and non front-line alectinib treatment groups.

For Phase 3 exploratory objectives, descriptive analyses will be conducted to evaluate the demographic, clinical and treatment characteristics among patients treated with lorlatinib. Results will be reported in aggregate. Categorical variables (e.g., ECOG performance status) will be reported as frequency and percentage. Continuous variables such as age will be reported as mean, standard deviation, median and range (minimum-maximum). In the case of missing observations, the number and percentage of missing values will be reported.

Clinical outcomes

ALK inhibitor DOT, OS, PFS will be assessed using the Kaplan-Meier method with 95% CIs, and summary tables of the number of events and censored patients at 3, 6, 12, 18, and 24 months. Further details about these calculations are presented below and in Table 1.

Clinical outcome results will be presented by study cohort and stratified by front-line alectinib and non-front line alectinib (pending sample size).

Overall survival (OS) will be defined as the interval between start date of alectinib to the date of death as documented in the LADMF and/or iKM EHR database. Patients who did not die will be censored on the study end date or the last visit date available in the database, whichever occurred first. In order to handle censoring, the Kaplan-Meier method will be used to calculate median overall survival with 95% confidence intervals (in number of months). Additionally, 3, 6, 12, 18, and 24-month survival probabilities will be reported. OS will be estimated for the full study population and stratified by study cohort. Log-rank tests will be used to assess statistical differences.

Duration of Therapy (DOT) for ALK inhibitors: An intent to treat approach will be used. DOT will be defined as duration of time (in months) between alectinib treatment initiation and discontinuation, or the last administration date of alectinib, or start date of a subsequent ALK inhibitor, initiation of any subsequent non-ALK inhibitor treatment (as a proxy for evidence of discontinuation), death or check-in in a hospice will be used as a stop date.

There may be some patients who do not have evidence of discontinuation or who do not move on to a subsequent therapy.

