Descriptive statistics (mean, median) and K-M methodology will be calculated from initiation of alectinib, until evidence of discontinuation for any reason, including but not limited to a treatment stop date, a last alectinib administration date, or evidence of new ALK inhibitor treatment or non-ALK inhibitor treatment. Patients who do not have evidence of discontinuing, starting new therapy, or whose last prescription date is <30 days from the end of the study period, will be censored at last visit date or end of study period.

$$DOT = (\frac{\textit{date of ALK treatment discontinuation - index date} + 1}{30.4375})$$

Progression-free survival: The PFS will be measured from the initiation of alectinib to the date of progression or date of death due to any cause, censoring patients who are still alive at the end of the study observation period and did not progress at the last visit date. Progression will be clinician-noted progression as noted per physician notes only, not by traditional Response Evaluation Criteria in Solid Tumors (RECIST) imaging, as this is impacted by frequency of imaging and may not be assessed the same across groups in daily clinical practice. Patients who did not progress or die will be censored on the study end date or the last visit date available in the database, whichever occurred first. The PFS will be estimated in months using the Kaplan-Meier method with 95% CIs, and summary tables of the number of events and censored patients at 3, 6, 12, 18, and 24 months. PFS will be estimated for the full study population and separately by study cohort. Log-rank tests will be used to explore statistical differences.

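### Alectinib duration of therapy is right-truncated in Cohorts C-E because entry requires a switch before the cut-off, and the duration of the next treatment (Objectives 3 and 7) is not defined

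*Combined protocol and SAP*

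**What the plan says.** Objectives 3 and 7 (Section 8) ask for two durations: "Estimate duration of therapy with alectinib and duration of therapy for post-alectinib treatment". Section 9.8 says that no separate statistical analysis plan will be written, so the protocol text has to define both.

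- **By-cohort reporting.** Table 1 (Section 9.4) names the variable "ALK inhibitor (alectinib and stratified by subsequent treatment) duration of therapy (DOT". Under Clinical outcomes, Section 9.8.3 lists DOT with OS and PFS for Kaplan-Meier analysis and adds: "Clinical outcome results will be presented by study cohort and stratified by front-line alectinib and non-front line alectinib (pending sample size".
- **Cohorts.** Section 9.8.3 has "Cohort C: Alectinib followed by treatment X (top 3 most frequent", with D and E built the same way, and "Cohort B (Alectinib only cohort): Alectinib treatment ongoing, or discontinued and no subsequent treatment".
- **Start and stop.** "DOT will be defined as duration of time (in months) between alectinib treatment initiation and discontinuation". Other stops are the last alectinib administration, the start of a subsequent ALK inhibitor, "initiation of any subsequent non-ALK inhibitor treatment (as a proxy for evidence of discontinuation", death and hospice entry. The Kaplan-Meier clock starts at alectinib initiation.
- **Formula.** The numerator is "date of ALK treatment discontinuation - index date" plus 1, divided by 30.4375. It does not say whether index date-1 or index date-2 is meant.
- **Next treatment.** Table 1 collects start and end dates of treatments after alectinib. Section 9.3 ties index date-2 to a next treatment during the observation period. The head of Table 1 ties it to the identification period.

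**The concern.** Membership of Cohorts C-E depends on the outcome being measured. A patient can be in C, D or E only if alectinib ended, and something else began, before data cut-off. Anyone with a long alectinib course still running at cut-off is excluded and placed in Cohort B. Kaplan-Meier handles right censoring. It does not repair a sample chosen because the event was already observed.

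Three consequences follow. DOT in C-E will look short whatever the true persistence. DOT in B will look long. The C-E figures will rise at the Phase 3 refresh merely because the window is longer. A reader could take any of these as information about alectinib or about a treatment sequence.

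The second half of Objectives 3 and 7 has a different problem. The plan never turns the collected next-treatment dates into a duration with a stated origin, event and censoring rule.

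**Working it through.** **1. Follow-up windows** (dates from Section 9.3, divisor 30.4375 from the DOT formula)

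- Phases 1/2 shortest: 30 Jun 2019 to 31 Dec 2019 = 184 days; 184/30.4375 = 6.05 months. This reproduces the minimum of 6 months' potential follow-up stated in Section 9.3.
- Phases 1/2 longest: 01 Jun 2017 to 31 Dec 2019 = 943 days = 31.0 months.
- Phase 3 shortest: 31 Aug 2020 to 31 Aug 2021 = 365 days = 12.0 months.
- Phase 3 longest: 01 Jun 2017 to 31 Aug 2021 = 1,552 days = 51.0 months.

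A C-E patient's alectinib DOT cannot exceed that patient's own window.

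**2. Size of the truncation**

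The documents give no DOT distribution, so these are assumptions:

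- The true median M is 25.7 months. This is the front-line trial PFS cited in Section 7, used as a stand-in for DOT. Values of 12, 18 and 36 were also tried.
- Follow-up C is uniform on the window [a, b].
- F(t) = 1 - 0.5^((t/M)^k), with k = 1 (exponential) or 0.8 to 1.5 (Weibull).

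The share seen to stop is P(T ≤ C). For k = 1 this is 1 - (e^(-λa) - e^(-λb))/(λ(b - a)), with λ = ln 2/25.7 = 0.02697:

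- Phases 1/2: 1 - (0.850 - 0.434)/0.6725 = 0.38.
- Phase 3: 1 - (0.724 - 0.253)/1.052 = 0.55.

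The median among those seen to stop is the x that solves P(T ≤ x, T ≤ C) = ½ P(T ≤ C):

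| True median (months) | k | Phases 1/2 | Phase 3 |
|---|---|---|---|
| 25.7 | 0.8 | 6.3 | 9.6 |
| 25.7 | 1 | 7.9 | 12.0 |
| 25.7 | 1.5 | 11.3 | 16.3 |
| 12 | 1 | 6.5 | 8.9 |
| 18 | 1 | 7.4 | 10.7 |
| 36 | 1 | 8.4 (simulation) | 13.0 |

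At M = 25.7 and k = 1, the proportion of stoppers with DOT beyond 12 months is 31% (Phases 1/2) and 50% (Phase 3), against a true 72%. Beyond 24 months it is 3% and 19%, against a true 52%. Both are planned reporting times.

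These figures describe everyone who stops. They carry over to switchers if switching is unrelated to DOT. If 60% of stoppers switch (assumption), 0.6 × 0.38 = 23% of patients have a next treatment, within the 20-30% in Section 9.6.

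**3. Cohorts A and B** (simulation, k = 1, 60% of stoppers switching)

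Keeping Cohort A whole and censoring ongoing patients gives a Kaplan-Meier median of 25.6 months in both windows against the assumed 25.7. In Cohort B the median is not reached in either window. With a true median of 12, Cohort B shows 22.5 months (Phases 1/2) and 17.9 (Phase 3).

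**4. C, D and E against one another**

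Suppose DOT has the same distribution for all, but one next agent is used only after 02 Nov 2018, and then by half of those who stop (assumption). Median prior alectinib DOT is then 10.9 against 6.8 months (Phases 1/2) and 14.3 against 10.4 (Phase 3), with no true difference.

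**5. Duration of the next treatment**

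| Needed | What the plan gives |
|---|---|
| Origin | Alectinib initiation in every DOT definition; an unnumbered index date in the formula |
| End date | An ALK treatment discontinuation date, which chemotherapy and immunotherapy (possible next treatments, Section 9.1) do not have |
| Event and censoring | Written for alectinib only |

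No data in the documents allow a value to be computed for this duration.

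**The case against.** The study is descriptive, and a cohort named as alectinib followed by another treatment already tells the reader that its members switched. Objectives 3 and 7 do not themselves ask for stratification. As a description of observed switchers the C-E figures are valid. That much stands. But they are labelled as alectinib DOT, estimated by Kaplan-Meier, and set beside Cohort B with no warning in the limitations (Section 9.10).

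Several stronger readings are tempting and should not be made:

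- *Cohort B is everyone else.* It is not. C-E cover only the three most frequent next treatments, so switchers to other agents are in Cohort A alone. The footnotes also allow B to be split.
- *A log-rank test of DOT between cohorts is planned.* Section 9.8.3 names log-rank for OS and PFS only. The p = 0.05 comparisons of ALK inhibitor sequences sit under patient and treatment characteristics. They can reach DOT, because Table 1 gives it the role of a treatment characteristic, but the plan does not say that they will.
- *Next-treatment duration would have the alectinib time added to it.* No section instructs this. The start of a subsequent ALK inhibitor stops the alectinib clock, and index date-2 is the natural origin for the next treatment. The duration is undefined; it is not shown to be overstated.
- *There is no end rule at all for later treatments.* Table 1 has a stop-date row (death or study end, or the start of the subsequent therapy). Its label could not be read in the text available, so its scope is uncertain.
- *Every C-E patient is an event without exception.* Read literally, the clause on a last prescription under 30 days from study end could censor someone who switched in the final month.

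**Conclusion.** The point holds in two parts.

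First, alectinib DOT in Cohorts C-E is right-truncated by the cohort definition and DOT in Cohort B is biased upward, while Cohort A is sound. The direction follows from the definitions, provided some patients are still on alectinib at cut-off. The size rests on assumptions: uniform entry, the chosen distribution, and a front-line PFS standing in for DOT when about half of the patients in the feasibility count were not front-line. At a true median of 25.7 months the median among all who stop is about 6-11 months in Phases 1/2 and 10-16 in Phase 3. At a true median of 12 the exponential figures are about 6.5 and 9. In every scenario run, the figure is below the truth and rises at the refresh without any change in persistence.

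Second, the DOT definition as written does not yield the duration of post-alectinib treatment that Objectives 3 and 7 require, least of all for chemotherapy or immunotherapy.

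**What to change.** (a) Report Kaplan-Meier alectinib DOT for Cohort A and by front-line/non-front-line only. For Cohorts C-E, report time on alectinib before switch, among observed switchers, as a description with no test between cohorts. Do not present Kaplan-Meier DOT in Cohort B as an estimate of alectinib persistence.

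(b) Define next-treatment DOT for any next treatment (ALK inhibitor, chemotherapy or immunotherapy) as (end date of that treatment - index date-2 + 1)/30.4375. Use the same event rules as alectinib DOT: documented stop or last administration, start of a further therapy, death or hospice entry. Censor ongoing patients at last visit or study end. Reconcile this with the stop-date row in Table 1 and state which treatments that row covers.

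(c) Reconcile index date-2 between Table 1 (identification period) and Section 9.3 (observation period). Using the observation period keeps patients who switch after identification closes.

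The cost is protocol wording and reprogramming; Table 1 already collects the dates. The by-cohort alectinib DOT curves, including Cohort B, and any test between them are given up.

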9.5. Data sources

Table 1 presents the data elements that will be evaluated through this study and their associated source. Most study data will originate from the EHR system of The US Oncology Network and Non-Network, iKM. Independent community-based oncology practices that participate in the Non-Network Select Program have implemented the iKM EHR, although the clinics are distinct from The US Oncology Network. iKM captures outpatient practice encounter histories for patients under community-based care, including, but not limited to patient demographics such as age and gender; clinical information such as disease diagnosis, diagnosis stages, performance status information and laboratory testing results; and treatment information, such as dosages and treatment administration within The US Oncology Network.

Structured data fields within the iKM EHR database will provide information needed to address most research questions. These data will be supplemented by additional unstructured data collected through chart review for a subset of the study population (selection methodology described in Section 9.3.4). Electronic chart review data will be collected by means of a secure, web-based electronic case report form (eCRF) by healthcare professionals with oncology experience.

The study will only use data from US Oncology Network practices utilizing full EHR capacities of iKM. Data management and administrative processing is supported by Ontada's quality assurance procedures. Additionally, iKM has previously been used to evaluate patient profiles, treatment patterns and outcomes among metastatic NSCLC patients and the results have been consistent with other published studies.[21-23] Thus the study team does not plan to conduct any additional studies to validate the accuracy of demographic, clinical, treatment and outcome information in the iKM EHR database.

The Limited Access Death Master File (LADMF) of the Social Security Administration will be an additional source of vital status (death), in addition to death dates recorded in the EHR. Common patient identifiers (patient identification, name, and birth date) will be used to link patients from the iKM data warehouse and iKM chart review. The social security number (SSN) will be used to link patients from iKM and LADMF data sources. All patients within iKM are assigned a unique patient identifier by iKM version (e.g., some large practices have separate installations by location). When linking to the LADMF, patient SSN is used. Some practices do not collect SSN and some patients may not report it. In all cases, reported deaths captured in iKM will supplement the Social Security Administration data.

Data from all sources and any derived variables will be merged into one master dataset for analysis. Data will be handled in compliance with the Health Insurance Portability and Accountability Act (HIPAA) and Health Information Technology for Economic and Clinical Health (HITECH).

9.6. Study size

A preliminary feasibility assessment for Phases 1 and 2 identified 293 patients who were treated with alectinib after 01 November 2017, with approximately half treated in the front-line setting. Of the 293 patients receiving alectinib, 74% (n=217) patients had an ALK result. Approximately 20-30% of the 293 patients received a subsequent therapy after alectinib. It is estimated that approximately 300 patients will be included in the Phase 2 structured data analysis. Targeted chart review for Phase 2 is proposed to occur on 150 patients receiving alectinib to identify at least 100 patients who received alectinib as front-line. In the event the total number of eligible patients following structured data screening exceeds the planned number of charts for review, a random sample will be selected.

For Phase 3 structured analysis, a preliminary feasibility assessment identified 521 patients who were treated with alectinib from 01 June 1 2017 through 31 December 2020. Chart review for Phase 3 will include patients who had ongoing treatment at the end of Phase 2

study period, and an additional 125 patients will be targeted to identify 100 new patient who received alectinib as front-line therapy. For Phase 3 exploratory analysis, a preliminary feasibility assessment identified 134 patients who were treated with lorlatinib from 01 November 2018 through 31 December 31 2020.

The final study population for analysis will be defined after identification and review of the patient population meeting the eligibility criteria in the iKM database. A specific power calculation will not be performed as this is a descriptive analysis.

